- 5) Intervention: All participants will either undergo cognitive training with neurofeedback via NIRS or be waitlisted. Participants will have 50% chance to undergo the cognitive training with neurofeedback; those in the waitlist group have the option to receive complimentary cognitive training with neurofeedback after completion of the study.

b. Procedure Risks

Neuropsychological assessment is a very low risk procedure and represents the only objective, valid and reliable method for accurately measuring cognitive function in humans. Neuropsychological assessment represents the standard of care for diagnosing cognitive impairments in children and adults.

Neuroimaging assessments using magnetic resonance imaging scans and NIRS are the most accurate and non-invasive, low-risk methods for determining neurobiological function in humans. Near-Infrared Spectroscopy has the additional benefit of not requiring the subject to endure loud noises or confined space for any period of time. This study will not employ any invasive neuroimaging techniques such as injection of contrast agents. MRI scans and NIRS measurements represent the only existing methods for obtaining accurate, *in vivo* measurements of the human brain.

c. Use of Deception in the Study

N/A

d. Use of Audio and Video Recordings

Video recording will occur. We will archive the data on the CIBSR server, which is housed in the CIBSR facility in the Department of Psychiatry and Behavioral Sciences. We will occasionally use images or footage in scientific presentations, but in such instances all identifying information will be eliminated or occluded. In such presentations, the recordings will be used to demonstrate the nature of the task and of our study procedure. The recordings will remain on the CIBSR secure server in archived form.

e. Alternative Procedures or Courses of Treatment

N/A

f. Will it be possible to continue the more (most) appropriate therapy for the participant(s) after the conclusion of the study?

N/A There are no treatments involved.

g. Study Endpoint(s)

N/A There are no treatments involved.

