5. PARTICIPANT POPULATION

a. Planned Enrollment

This research study is looking for 160 participants with ADHD.

b. Age, Gender, and Ethnic Background

Participants (males and females) ages 7-11 years of all ethnic backgrounds will be recruited.

c. Vulnerable Populations

We have already tested the efficacy of the proposed cognitive training in healthy young adults in previous phases of the study. We will be studying minors because, in the future, neurofeedback and cognitive control paradigms are likely to benefit still-developing minors most, due to the increased plasticity associated with early neurodevelopmental processes. Thus, we hope to specifically address the applicability of neurofeedback scenarios in developing populations. We will be taking special precautions to protect the rights of these minors, including following well-established protocols for parental consent and assent.

d. Rationale for Exclusion of Certain Populations

N/A

e. Stanford Populations

Laboratory personnel and students may be subjects in piloting phases.

f. Healthy Volunteers

Participants will be children with ADHD.

Parents and subjects will be asked to notify research staff immediately if they encounter any problems and participation can be discontinued at any time..

g. Recruitment Details

Subjects will be identified using established recruitment measures used at the Center for Interdisciplinary Brain Sciences Research. These procedures include advertising online, including on ResearchMatch, or in local newspapers and posting notices in public places. These procedures also include email messages to email lists and to potential participants.

h. Eligibility Criteria

i. Inclusion Criteria

Meeting diagnostic criteria for ADHD, determined by a BRIEF Working Memory score ≥ 65 . Age range: 7 years - 11 years.

ii. Exclusion Criteria

Presence of contraindications for MRI (orthodontia, vascular stents, metallic ear tubes, metal implants, pregnancy, etc) for those participating in an MRI scan. History of serious medical, neurological or psychiatric illness (except disorders of interest) or sensory impairment.

i. Screening Procedures

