Potential participants will be screened for inclusion and exclusion criteria via an online and/or telephone screen (see attachments). Only information necessary to ascertain eligibility will be requested. Because the screening will include questions involving medical history to determine diagnosis of ADHD, a limited waiver of authorization will be requested in section 15.

j. Participation in Multiple Protocols

The screening questionnaire will include a question regarding other study participation. Participants can be enrolled in other studies that do not involve medications or substances which would affect the MRI and NIRS measurements or cognitive interventions. Each case will be evaluated individually prior to enrollment.

k. Payments to Participants

Participants will be provided with up to \$300 for their participation. If the participant does not complete the all study visits, he will be reimbursed \$20/hr for the portion of the study that he has completed.

l. Costs to Participants

None

m. Planned Duration of the Study

The study will require approximately 5 years to complete. Total time per participant: 10-15 minutes for screening, 30 minutes for consent, 30-60 minutes for each neuropsychological testing session, 1 hour for NIRS (or MRI) measurements. Analysis of participant data will require approximately 18 hours per participant.

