A Novel Neuromonitoring Guided Cognitive Intervention for Targeted Enhancement of Working Memory

Statistical Analysis Plan

NCT04002167

August 25, 2023

The statistical analysis was computed in RStudio (R version 4.3.0) and the linear mixed-effect models for each behavioral dataset were constructed in lmer package to handle the missing data points. The analysis incorporated the interaction between group and session as a fixed effect, accounting for age, sex, and medication effects, while subject IDs were treated as a random effect in the model.

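### The only within-child covariance term is a subject random effect; with three or more sessions the group-by-session standard error can be wrong in either direction, depending on a contrast the SAP does not name.

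*SAP*

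**What the plan says.** The SAP is one paragraph. It says that "linear mixed-effect models for each behavioral dataset were constructed in lmer package to handle the missing data points". It says the analysis "incorporated the interaction between group and session as a fixed effect", "accounting for age, sex, and medication effects", and that "subject IDs were treated as a random effect in the model". It mentions no random slope, residual correlation structure, session-specific variance or robust standard error. It does not say whether session is a factor or a number, whether the interaction is tested as a whole or through one contrast, or at what significance level.

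The protocol does not fill these gaps. Section 5.m allows "30-60 minutes for each neuropsychological testing session", which implies repeated testing but gives no count. Section 2.g lists study endpoints as not applicable. Section 5.a gives the size ("This research study is looking for 160 participants with ADHD") and section 2.a the allocation ("Participants will have 50% chance to undergo the cognitive training with neurofeedback").

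**The concern.** A subject ID entered as a single random effect in lmer is normally a random intercept. That model treats every pair of sessions as equally correlated and every session as equally variable. Around a training course neither need hold. Scores further apart in time may correlate less, and children may differ in how much they respond.

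The model applies one pooled within-child variance to every contrast. If the correlations differ, that variance is too small for some contrasts and too large for others. Group by session is the only group comparison in the SAP, so the error would fall on the efficacy result. The SAP also relies on this model for missing data, and likelihood handling of missing scores depends on the covariance being right.

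**Working it through.** The plan gives no significance level, power or sample-size calculation, so there is no figure of its own to reproduce.

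**Inputs.** From the documents: 160 children, 1:1, so 80 per arm (used only for the omnibus simulation). Assumed: two-sided 5%; 2 to 5 sessions (T); complete data and equal variances unless stated; AR(1) correlation r of 0.6 to 0.8 between adjacent sessions.

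**Formula.** With balanced data and unit variances, the random-intercept model estimates the within-child variance as 1 − ρ̄, where ρ̄ is the mean of all pairwise correlations. It gives any between-session change a variance proportional to 2(1 − ρ̄). The true value for sessions j and k is 2(1 − ρ_jk). Hence

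- SE ratio (model/true) = √[(1 − ρ̄)/(1 − ρ_jk)]
- type I error = 2[1 − Φ(1.96 × SE ratio)]

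Sample size cancels.

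**Example, T = 3, r = 0.7.** The correlations are 0.70, 0.70 and 0.49, so ρ̄ = 1.89/3 = 0.63.

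- Baseline to last: √(0.37/0.51) = 0.852; 1.96 × 0.852 = 1.67; type I error 9.5%.
- Baseline to next: √(0.37/0.30) = 1.111; 1.96 × 1.111 = 2.18; type I error 3.0%.

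**Results for r = 0.6 to 0.8.**

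| Sessions | Baseline to last: SE ratio | Type I error | Baseline to next: SE ratio | Type I error |
|---|---|---|---|---|
| 2 | 1.00 | 5.0% | 1.00 | 5.0% |
| 3 | 0.87 to 0.84 | 9.0 to 10.0% | 1.10 to 1.13 | 3.2 to 2.7% |
| 4 | 0.83 to 0.79 | 10.3 to 12.4% | 1.17 to 1.23 | 2.2 to 1.6% |
| 5 | 0.83 to 0.76 | 10.5 to 13.4% | 1.22 to 1.31 | 1.7 to 1.0% |

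**Other covariances.** For these, 1 − ρ̄ is replaced by the general pooled within-child variance tr(MΣ)/(T − 1), where M is the centring matrix, and the true contrast variance by c′Σc.

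- Compound symmetry (0.6): 5.0% for every contrast and every T.
- Random slopes (intercept and residual variance 0.5 each; slope variance 0.05 or 0.2): baseline to last 6.1% or 8.4% with three sessions and 7.9% or 13.1% with four; baseline to next 4.5% or 3.4%, and 3.9% or 2.1%.
- Correlation 0.6 with baseline SD 0.8 of the later SDs, three sessions: baseline to last 4.4%.
- If session is coded as a number, the test is a linear trend. Under AR(1) 0.5 to 0.9 its type I error is 8.4 to 10.5% with three sessions and 11.3 to 16.0% with four.

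**Omnibus F test.** Simulated with 80 per arm, no covariates and 20,000 replicates per setting, under AR(1) 0.5 to 0.9 or slope variance 0.2: about 5.3 to 5.7% with three sessions and 5.7 to 6.9% with four. Under compound symmetry it is 5.1 to 5.2%.

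**Missing data, two sessions.** This is a deliberately adverse large-sample check: correlation 0.6, 30% dropout at the second session driven by baseline in opposite directions in the two arms (log-odds slope 1 to 1.5 per baseline SD), and post-training SD 0.8 or 1.25 times baseline. The true regression of post on baseline is 0.6 × 0.8 = 0.48 or 0.6 × 1.25 = 0.75. The common-variance model forces that slope to equal its single fitted correlation (about 0.61 to 0.63, or 0.55 to 0.56), so it projects the missing scores wrongly. The interaction is biased by about 0.07 to 0.13 baseline SD. With equal variances the bias is essentially zero.

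**The case against.** The strongest reply is that three sessions are not established. The protocol's train-or-wait design fits a plain pre/post comparison, and with two complete sessions the stated model is exact. This stands, and it makes the standard-error part of the point conditional. It does not remove the missing-data part.

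A reader might infer that the plan's type I error exceeds 5%. The documents do not support that. They state no session count, contrast or significance level, and the SAP neither says intercept-only nor rules out a random slope. The direction also reverses. If training ends at the second of three sessions and the third is a follow-up, baseline to post-training is the adjacent contrast, and the test is conservative. Under compound symmetry there is no error at all.

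A reader might also infer that an omnibus interaction test wastes power. If a single contrast has 80% power and its noncentrality (7.85) stays the same as sessions are added, the omnibus test has 71% with three sessions and 65% with four. But an effect that appears after training and persists gives the omnibus test about 83% with three sessions under compound symmetry. The loss is not general, and the SAP does not say that an omnibus test is used.

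Finally, the SAP is written in the past tense, so changing the model now could be a post hoc choice. That stands and shapes the fix.

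**Conclusion.** The point holds conditionally. The SAP leaves open the number and coding of sessions, the tested contrast and all covariance structure beyond a subject random effect, so type I error control for its only group comparison cannot be verified.

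Given a random intercept, at least three sessions and non-constant correlation, the error is material. For a nominal 5% test it runs from about 2% to 12% with three or four sessions under AR(1) 0.6 to 0.8, depending on the contrast. The bias with two sessions needs both unequal variances and baseline-dependent dropout that differs between arms, and its size comes from an adverse illustration. The correlation, variance and dropout values are all assumptions. This is worth correcting because the remedy is cheap and works in both directions; it is not evidence that the reported result is wrong.

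**What to change.** State the number and timing of sessions. Fit session as a factor with an unstructured within-child covariance (session-specific variances and general correlation), for example with gls or an MMRM routine. Test one named 1-df contrast: training minus waitlist in change from baseline to the post-training session.

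Alternatively, keep the lmer fit and report small-sample cluster-robust standard errors by child. That corrects the standard errors but not bias from missing data.

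If results are already known, label the re-run as a sensitivity analysis.

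The cost is SAP wording, a re-run and a few more covariance parameters: T(T + 1)/2, so 6 with three sessions or 10 with four, against 2 for a random intercept. That is manageable with 160 children planned. No new data are needed. Intervals may become wider or narrower. With two sessions essentially nothing is lost.
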